Overview of Study Design: Eligible patients will be entered onto the study and receive oral ixazomib weekly. A window period of six 4-week cycles of ixazomib monotherapy will be given upfront. On completion of the window period, four weekly doses of intravenous rituximab infusions will be added as ixazomib is continued. Treatment with ixazomib will continue on 4-week cycles until unacceptable drug toxicity, disease progression, or other reason as described below. The ORR of ixazomib monotherapy during the window period will be calculated before the addition of rituximab. The null hypothesis for ixazomib monotherapy in the upfront setting is an ORR < 40% and the alternative hypothesis is that the ORR exceeds 60%. A total of 36 patients will be treated.
Study Population: The study population will include patients with a diagnosis confirmed histopathologically or by flow cytometry of indolent B-NHL, including the subtypes CLL/SLL, FL, MCL, MZL, and WM/LPL. Patients will not have received standard systemic therapy for their B-NHL previously, except in cases of the MALT subtype of MZL treated with antibiotics. At the time of enrollment, patients will have measurable disease and a clinical indication for treatment.
Duration of Study: Anticipated enrollment period is 1-2 years, with total study time of approximately 5 years.

STUDY OVERVIEW DIAGRAM

SCHEDULE OF EVENTS

Study Calendar: One treatment cycle = 28 days

Required Procedures	Screening ⁶	Treatment Phase	End of Treatment ¹²
History and Physical			
Medical history	x		
Physical exam	x	X ⁹	x
ECOG performance status	x	X ⁹	x
Clinical disease assessment	x	X ⁹	x
Adverse event assessment	x	X ⁹	x
Labs and Imaging			
CBC and differential	X	X ¹⁰	X
Comprehensive metabolic panel	X	X ¹⁰	X
LDH	X	X ¹⁰	X
Beta 2 Microglobulin	X		
SPEP and immunofixation ¹	X	X ¹¹	X
CT chest, abdomen, pelvis ²	X	X ¹¹	X
FDG-PET (base of skull to proximal femur) ³	X	X	
Bone marrow studies ⁴	X	X	
Pregnancy test	X ⁷		
Pathologic studies	X ⁸	X ⁸	
Tumor Assessment ⁵	X	X ¹¹	X

¹ In cases of WM/LPL.

² In cases of radiographically measurable disease (see section 7.2). Note this may not be present for cases of CLL and WM. Imaging of the neck is suggested for clinically evident or previously described cervical disease.

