3. STUDY ENDPOINTS

3.1 Primary Endpoints

Overall response rate (CR + PR)

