7.1.1 Determination of Sample Size

The sample size was determined to gain a preliminary assessment of the efficacy of ixazomib in untreated subtypes of B-NHL. The ORR for effective single-agent therapy in patients with indolent B-NHL is approximately 40 to 70% [19]. In this single-stage phase II study, the null hypothesis that the true response rate is $\leq 40\%$ will be tested against the alternative hypothesis that the true response rate is $\geq 60\%$ with a type I error rate of 8% and a power of 85%. An ORR of at least 19 out of 36 will be required to conclude promising efficacy.

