7.3 Primary Efficacy Endpoint

Response assessments will be performed by the investigators. All measurable disease should be documented at screening and re-assessed at each subsequent tumor evaluation.

All patients treated with ixazomib will be considered evaluable for assessment of

response, with the following exceptions: 1) patients who missed $\geq 50\%$ of scheduled doses of ixazomib prior to first scheduled treatment-phase tumor evaluation, unless due to related AE or progressive disease, will not be considered evaluable for assessment of response; 2) patients who did not undergo scheduled treatment-phase tumor evaluation, unless due to progressive disease, will not be considered evaluable for assessment of response.

The primary efficacy endpoint is the overall response rate (CR + PR for CLL/SLL, FL, MZL, and MCL; CR + Very Good PR + PR + Minor Response for WM/LPL) as assessed by the investigators. ORR will be calculated for all treated patients for each disease cohort. The corresponding 95% two-sided confidence interval will be derived.

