7.4 Secondary Efficacy Endpoints

7.4.1 Duration of Response

In each disease cohort, for subjects achieving objective response as assessed by investigators, their duration of response as assessed by investigators will be calculated to determine durability. Duration of response will be measured from the time by which the measurement criteria are met for CR or PR, whichever is recorded first, until death or the first date by which recurrent or progressive disease is objectively documented. Subjects who are progression-free and alive at the time of clinical cut-off, or have unknown status will be censored at the last tumor assessment.

Non-responders will be excluded from the analysis of DOR. Kaplan Meier methodology will be used to estimate event-free curves.

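### Sections 3.1 and 7.3 define the primary response differently for WM/LPL, and Section 7.1.1 does not say which definition the 40%/60% rates and the 19-of-36 rule use

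*Combined protocol and SAP*

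**What the plan says.** Section 3.1 lists the primary endpoint as "Overall response rate (CR + PR"), with no exception by histology. Section 7.3 keeps CR + PR for CLL/SLL, FL, MZL and MCL, but for WM/LPL counts "CR + Very Good PR + PR + Minor Response for WM/LPL". Appendix 11.10 defines Minor Response as a serum IgM reduction of at least 25% but less than 50%; PR needs at least 50% and Very Good PR at least 90%.

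Section 7.1.1 sets a single test of one response rate, 40% against 60%, "with a type I error rate of 8% and a power of 85" percent. The decision rule is "An ORR of at least 19 out of 36 will be required to conclude promising efficacy". The benchmark sentence reads "The ORR for effective single-agent therapy in patients with indolent B-NHL is approximately 40 to 70% [19]" and names no response categories. The Protocol Summary repeats the hypotheses ("The null hypothesis for ixazomib monotherapy in the upfront setting is an ORR < 40" percent) without adding a definition.

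Section 7.4.1 states: "Duration of response will be measured from the time by which the measurement criteria are met for CR or PR, whichever is recorded first". It covers subjects with an objective response, a term it does not define, and excludes non-responders. Section 7.2.3 applies the Lugano criteria to WM/LPL with known or suspected nodal disease, while Section 7.2.5 applies the WM workshop criteria to WM/LPL.

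**The concern.** Success rests on one pooled count, and the plan gives two rules for what enters it. A WM/LPL patient with, say, a 30% IgM fall and no new symptoms or signs adds nothing to the count under 3.1 and adds one under 7.3. The conclusion could then turn on which section the analyst follows and on how many WM/LPL patients happen to enrol, since entry is not stratified (Section 7.1.2) and the plan sets no WM/LPL quota or cap.

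The second issue is the meaning of the null. A 40% rate of CR + PR and a 40% rate that includes minor responses are different hypotheses. If the rate is on one scale and the count is on the other, the stated type I error and power do not describe the test that is carried out.

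The third is a gap in a secondary endpoint: 7.3 can create a responder for whom 7.4.1 supplies no start date.

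**Working it through.** **1. The plan's own figures.** Inputs from Section 7.1.1: n = 36, success at 19 or more responses, p0 = 0.40, p1 = 0.60. The plan does not state sidedness, but the rule is one-sided. The exact binomial gives:

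- P(X ≥ 19 | 36, 0.40) = 0.0826
- P(X ≥ 19 | 36, 0.60) = 0.8540

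Both round to the stated 8% and 85%, so the design reproduces.

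**2. How close one patient is to the decision.** P(X ≥ 18 | 36, 0.40) = 0.1460, so P(X = 18) = 0.1460 − 0.0826 = 0.0633. At a 40% rate the trial ends exactly one response short 6.3% of the time. One reclassified WM/LPL patient then changes the conclusion.

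**3. Effect on the false-positive chance, if the 40% null means CR + PR.** Let w be the number of WM/LPL patients and m the chance that a WM/LPL patient's best response is minor. Neither is in the documents; both are assumptions. With a CR + PR rate of 40% in every histology, the 7.3 count is the sum of Binomial(w, 0.40 + m) and Binomial(36 − w, 0.40). The pooled expected rate is 0.40 + m·w/36.

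| w | m | Pooled rate | P(count ≥ 19) |
|---|---|---|---|
| 0, or any w with m = 0 | – | 40.0% | 8.26% |
| 2 | 10% | 40.6% | 9.3% |
| 4 | 10% | 41.1% | 10.5% |
| 6 | 20% | 43.3% | 16.2% |
| 7 | 20% | 43.9% | 17.9% |
| 10 | 30% | 48.3% | 35.1% |

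**4. If the 40% null is on the 7.3 definition.** The true rate of what is counted is then 40% by hypothesis, and P(count ≥ 19) is 8.26% whatever w and m are.

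**5. Which scale the documents suggest.** Section 3.1 says CR + PR. The 40 to 70% benchmark cites reference 19, whose listed title concerns follicular lymphoma, and the Lugano table for FL in Appendix 11.8 has no Minor Response category. Both point to CR + PR, but Section 7.1.1 does not say so.

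**6. Who can be a minor responder.** Section 7.2.3 assigns Lugano criteria to WM/LPL with nodal disease, and Lugano has no such category. Section 7.2.5 assigns the WM criteria with no nodal exception. The plan does not say which governs when both apply, so m may not apply to all w patients in step 3.

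**7. Duration of response.** Very Good PR causes no gap, because an IgM fall of at least 90% also meets the 50% PR threshold. A minor responder who later reaches PR gets a start date at that point. The gap is confined to WM/LPL patients whose best response is minor: they are responders under 7.3, so the exclusion of non-responders does not clearly remove them, yet they never meet the 7.4.1 start rule.

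**The case against.** The best defence is that 7.3 is deliberate. Response is assessed by subtype (Section 7.2.1), WM/LPL has its own criteria, those criteria list Minor Response as a category, and 7.3 spells out the count histology by histology. Section 3.1 can be read as shorthand. A percentage fall in IgM is also not on the same scale as nodal measurements or lymphocyte counts, so the pooled rate mixes criteria with or without Minor Response. Section 7.3 reports ORR by disease cohort with a confidence interval, so a WM/LPL contribution would be partly visible.

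Much of this stands. Nothing in the documents shows that 3.1 should override 7.3. With the document dated December 2023 and response assessed by the investigators in a single-arm trial, narrowing the endpoint now could itself look data-driven. None of it tells the analyst which count meets the 19-of-36 rule, however, and cohort-level rates do not settle a pooled decision.

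A reader might infer something stronger: that counting minor responses breaks the 8% type I error. The documents do not support that as a fact. It requires the 40% null to be on the CR + PR scale, which is plausible but not stated, and at least one WM/LPL patient with a real chance of a minor response. Neither the WM/LPL share nor the minor-response rate is given.

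**Conclusion.** The inconsistency is in current text and should be fixed. The primary endpoint has two definitions that differ for WM/LPL, and the hypotheses and the decision rule are tied to neither. One patient whose best response is minor can move the result across the threshold.

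The effect on the false-positive chance is conditional. On a CR + PR null it runs from none (8.26%) through 9.3% to 17.9% in the small and middle scenarios, up to 35.1% with 10 WM/LPL patients and a 30% minor-response rate. These figures assume a 40% CR + PR rate in every histology and that every WM/LPL patient can be scored as a minor responder, which Section 7.2.3 leaves in doubt. On a null set for the 7.3 definition, alpha stays at 8.26%.

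The duration-of-response gap is real but narrow, in a descriptive secondary endpoint. This is a point that should be fixed; confidence in the contradiction is high, and in the size of its effect medium.

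**What to change.** - Use one ORR definition in Sections 3.1, 7.1.1 and 7.3.
- State in 7.1.1 that the 40% and 60% rates and the 19-of-36 rule apply to that definition. If Minor Response is kept, add that the 8% holds only for a 40% null on the wider definition.
- Whichever definition is chosen, report the pooled count against 19/36 both with and without WM/LPL minor responses.
- State which response criteria govern WM/LPL with known or suspected nodal disease, reconciling 7.2.3 with 7.2.5.
- State in 7.4.1 that duration of response is limited to patients with PR or better and starts at the first PR or better.

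The cost is a few sentences and one extra analysis line. No new data are needed. The pooled CR + PR figure may be slightly lower than the 7.3 figure, by the number of WM/LPL patients whose best response is minor. Reporting both counts avoids the appearance of choosing a definition after seeing the data.

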7.4 Secondary Efficacy Endpoints

7.4.1 Duration of Response

In each disease cohort, for subjects achieving objective response as assessed by investigators, their duration of response as assessed by investigators will be calculated to determine durability. Duration of response will be measured from the time by which the measurement criteria are met for CR or PR, whichever is recorded first, until death or the first date by which recurrent or progressive disease is objectively documented. Subjects who are progression-free and alive at the time of clinical cut-off, or have unknown status will be censored at the last tumor assessment.

Non-responders will be excluded from the analysis of DOR. Kaplan Meier methodology will be used to estimate event-free curves.

7.4.2 Progression Free Survival

PFS will be measured for each disease cohort as time from the first study drug administration to the first occurrence of lymphoma progression or death from any cause.

Data for subjects without disease progression or death will be censored at the date of the last tumor assessment. Kaplan-Meier methodology will be used to estimate the event-free curves.

7.4.3 Time to Additional Anti-neoplastic Treatment

For each disease cohort the time to additional anti-neoplastic treatment will be measured from the time of first study drug administration until the date of subsequent the first subsequent therapy given to treat the B-NHL. Data for subjects that have not received additional anti-neoplastic therapy will be censored at the date of last known contact.

7.4.4 Pharmacokinetics/Pharmacodynamics/Biomarkers

Biomarker data may be collected on all subjects enrolled on study and examined for correlation of response to ixazomib in aggregate and with independent cohorts.

Samples of tumor tissue (fresh or formalin-fixed, paraffin-embedded) may be analyzed by immunohistochemistry to evaluate expression of proteins NF-KB p65,

p21, CD68, and PSMA5. Samples of peripheral blood and tumor tissue (fresh or formalin-fixed, paraffin-embedded) may additionally be studied using by SNP genotyping for PSMB1 P11A and with gene expression profiling to characterize candidate lesions particular to cell-cycling and proliferation pathways. Clinical features and validated prognostic data including cytogenetics for CLL/SLL, the MIPI score and Ki-67 scores for MCL, the FLIPI score for MZL and FL, and the IPSS score for WM/LPL will be scored and analyzed for their impact on response to ixazomib in independent cohorts only.

7.4.5 Safety Analysis

Adverse events and serious adverse events as defined in section 8 will be reviewed internally on an ongoing basis to identify safety concerns. Safety data will be evaluated in aggregate across the study cohorts. Analysis of safety data will be conducted on the safety population, which includes enrolled subjects who receive at least 1 dose of ixazomib. Safety summaries will include tabulations in the form of tables. The frequency of treatment-emergent AE's will be summarized. Additional AE summaries will include AE frequency by AE severity and relationship to the study drug.

AE's requiring discontinuation of the study drug will be summarized separately, both overall and by AE severity and by relationship to the study drug. Clinically significant abnormal laboratory values will be summarized over study visits.

8. ADVERSE EVENTS

8.1 Definitions

8.1.1 Adverse Event Definition

Adverse event (AE) means any untoward medical occurrence in a patient or subject administered a pharmaceutical product; the untoward medical occurrence does not necessarily have a causal relationship with this treatment. An AE can therefore be any unfavorable and unintended sign (including an abnormal laboratory finding), symptom, or disease temporally associated with the use of a medicinal (investigational) product whether or not it is related to the medicinal product. This includes any newly occurring event, or a previous condition that has increased in severity or frequency since the administration of study drug.

An abnormal laboratory value will not be assessed as an AE unless that value leads to discontinuation or delay in treatment, dose modification, therapeutic intervention, or is considered by the investigator to be a clinically significant change from baseline.

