⁹ Clinical assessment (physical exam including performance status, adverse event and clinical disease assessment) will be performed on Day 1 of each cycle (+/-3 days) through the first 8 cycles. After cycle 8, clinical assessments will be performed on Day 1 of each odd-numbered cycle (+/-6 days). For Cycle 1, Day 1, the screening clinical assessment may be used. A Cycle 1, Day 14 (+/-3 days) clinical assessment is strongly recommended.

¹⁰ Labs will be performed on Day 1 (+/-3 days) of each cycle for the first 8 cycles. After cycle 8, labs will be performed on Day 1 (+/-6 days) of each cycle. Labs may be performed at local laboratories with appropriate review by the PI/ Sub-I. For Cycle 1, Day 1, labs performed within 14 days are acceptable. Cycle 1, Day 14 (+/-3 days) labs are strongly recommended.

¹¹ Treatment phase tumor evaluation labs and/or imaging will be performed every 8 weeks of therapy (+/- 6 days) during the first 32 weeks, and approximately every 16 weeks of therapy thereafter, or as indicated per clinical standard of care (e.g. as appropriate for disease, to evaluate clinical suspicion of disease progression).

¹² End-of-treatment evaluations should be done within 30 days of the last dose of ixazomib or prior to the start of a new anti-neoplastic drug, whichever is first. Tumor assessment labs and/or imaging will be performed at end-of-treatment evaluation only for subjects who did not have tumor assessment labs and/or imaging performed within 60 days of end-of-treatment.

Long-term follow-up should be done according to the patient's physicians standard of care. This may be performed at the patient's local physician's offices. Long-term follow-up will assess survival and disease progression; for clarification, subjects may be contacted by the study team until death, withdrawal of consent, lost to follow-up, or study termination by the sponsor-investigator, whichever occurs first.

Table of Contents

PROTOCOL SUMMARY	2
STUDY OVERVIEW DIAGRAM	3
SCHEDULE OF EVENTS.....	4
LIST OF ABBREVIATIONS AND GLOSSARY OF TERMS	8
1. BACKGROUND AND STUDY RATIONALE	12
1.1 Scientific Background	12
1.1.1 Disease Under Treatment	12
1.1.2 Ixazomib	12
1.2 Preclinical Experience	12
1.3 Clinical Experience	12
1.4 Pharmacokinetics and Drug Metabolism	13
1.5 Clinical Trial Experience Using the Oral Formulation of Ixazomib	14
1.6 Relapsed and/or Refractory Multiple Myeloma	20
1.7 Newly Diagnosed Multiple Myeloma (NDMM).....	21
1.9 Study Rationale	21

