3.2 Secondary Endpoints

Efficacy

- Duration of response (DOR)
- Progression-free survival (PFS)
- Overall survival (OS)
- Complete response rate (CR)
- Time to next antineoplastic therapy (TNT)

Safety/Tolerability

- Frequency, severity, and relatedness of adverse events (AEs)
- Frequency of AEs requiring discontinuation of study drug or dose reductions

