6.4 Dose-Modification Guidelines

Study drug dose modifications may change depending on the disease and combination with other drug(s).

If a new combination study, an attempt should be made to integrate dose modifications for the combination for each AE.

6.4.1 Recommended Ixazomib Criteria for Beginning or Delaying a Subsequent Treatment Cycle & Dose Modifications for Treatment Associated Toxicity

Treatment with ixazomib will use a cycle length of 28 days. For a new cycle of treatment to begin, the patient must meet the following criteria:

- ANC must be $\geq 500/\text{mm}^3$.
- Platelet count must be $\geq 50,000/\text{mm}^3$.
- Non-hematologic toxicities, attributable to ixazomib (except for alopecia) and which required a dose hold, should, at the physician's discretion, generally be recovered to \leq Grade 1 or the patient's baseline condition.

If the patient fails to meet the above-cited criteria for initiation of the next cycle of treatment, dosing should be delayed for 1 week. At the end of that time, the patient should be re-evaluated to determine whether the criteria have been met. If the patient continues to fail to meet the above-cited criteria, delay therapy and continue to reevaluate. The maximum delay before treatment should be discontinued will be 3 weeks or at the discretion of the Principal Investigator and/or Sub-Investigator.

For dosing recommendations upon recovery, refer to Table 6-2 and Table 6-3.

Table 6-1 Ixazomib Dose Adjustments

Dose Level	Dose (mg)
Starting Dose	4.0 mg
-1	3.0 mg
-2	2.3 mg
-3	Discontinue

Dosage adjustments for hematologic toxicity are outlined in Table 6-2.

Table 6-2 Ixazomib Dose Adjustments for Hematologic Toxicities

Criteria	Action
Platelet count less than 30,000/mm ³	
 • Hold Ixazomib dose. • Once the platelet counts have met the prespecified values (see Section 6.4.1), ixazomib may be reinitiated at its most recent dose. • If platelet count falls to less than 30,000/mm³, hold ixazomib until counts have met the prespecified values (see Section 6.4.1) and then resume ixazomib at the next lower dose.

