events that pose a threat to a patient's life or ability to function. A severe AE (Grade 3 or 4) does not necessarily need to be considered serious. For example, a white blood cell count of $1000/\text{mm}^3$ to less than 2000 is considered Grade 3 (severe) but may not be considered serious. Seriousness (not intensity) serves as a guide for defining regulatory reporting obligations.

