8.2 Procedures for Reporting Serious Adverse Events

Adverse Events may be spontaneously identified by the patient and/or in response to an open question from study personnel or revealed by observation, physical examination, or other diagnostic procedures. Any clinically relevant deterioration in laboratory assessments or other clinical finding is considered an AE. When possible, signs and symptoms indicating a common underlying pathology should be noted as one comprehensive event. For serious AEs, the investigator must determine both the intensity of the event and the relationship of the event to study drug administration. For serious pretreatment events, the investigator must determine both the intensity of the event and the relationship of the event to study procedures.

Adverse Events which are **serious** must be reported to Millennium Pharmacovigilance (or designee) from the date the participant signs Informed Consent through 30 days after administration of the last dose of ixazomib. Any SAE that occurs at any time after completion of ixazomib treatment or after the designated follow-up period that the sponsor-investigator and/or sub-investigator considers to be related to any study drug must be reported to Millennium Pharmacovigilance (or designee). In addition, new primary malignancies that occur during the follow-up periods must be reported, regardless of causality to study regimen, for a minimum of three years after the last dose of the investigational product, starting from the first dose of study drug. All new cases of primary malignancy must be reported to Millennium Pharmacovigilance (or designee).

Planned hospital admissions or surgical procedures for an illness or disease that existed before the patient was enrolled in the trial are not to be considered AEs unless the condition deteriorated in an unexpected manner during the trial (e.g., surgery was performed earlier or later than planned). All SAEs should be monitored until they are resolved or are clearly determined to be due to a patient's stable or chronic condition or intercurrent illness(es).

Since this is an investigator-initiated study, the principal investigator [name]., also referred to as the sponsor-investigator, is responsible for reporting serious adverse events (SAEs) to any regulatory agency and to the sponsor-investigator's EC or IRB.

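### Laboratory abnormalities that force no action reach the safety results only through an undefined investigator judgment, so cytopenia rates can be understated by an amount the plan cannot show

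*Combined protocol and SAP*

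**What the plan says.** Safety is a secondary objective (section 2.2). Section 3.2 measures it by how often AEs occur, how severe they are and whether they are related, and by the AEs that lead to stopping or reducing the drug.

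Section 8.1.1 sets the entry rule for laboratory values: "An abnormal laboratory value will not be assessed as an AE unless that value leads to discontinuation or delay in treatment, dose modification". The sentence goes on to admit values that lead to therapeutic intervention, and finally any value that "is considered by the investigator to be a clinically significant change from baseline". Section 8.2 adds a similar rule: "Any clinically relevant deterioration in laboratory assessments or other clinical finding is considered an AE".

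Section 7.4.5 builds the AE tables on AEs as section 8 defines them. Its one laboratory output is this: "Clinically significant abnormal laboratory values will be summarized over study visits". None of these sections defines clinically significant or clinically relevant. Appendix 11.11 names CTCAE 4.0 for AE reporting, and no section plans to apply it to all collected values.

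The data are scheduled. For CBC with differential, metabolic panel and LDH, footnote 10 of the Schedule of Events says: "Labs will be performed on Day 1 (+/-3 days) of each cycle for the first 8 cycles". Day 1 testing continues in every later cycle with a wider window, and a Cycle 1 Day 14 draw is strongly recommended.

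**The concern.** Both routes by which a laboratory value can enter the safety results pass through the same filter: something was done about it, or the investigator judged that it mattered. For values that force no action, only the judgment remains. The study is open-label and single-arm, and the plan gives no criterion, so two investigators could record the same count differently.

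What is at stake is the reported frequency and severity of cytopenias and chemistry abnormalities, for a drug whose rationale (section 1.9) rests partly on good tolerability. The plan contains no objective laboratory analysis against which the judged rates could be compared.

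**Working it through.** The plan states no figure on this point, so there is none to reproduce. The check has three steps.

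**1. Which Day 1 values force an action?** Inputs are the cycle-start criteria (section 6.4.1), the hold triggers (Table 6-2) and the eligibility floors (section 5.1), all per mm³.

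| Scheduled Day 1 value | Cycle-start criterion | Hold trigger | Eligibility floor | Forced action |
|---|---|---|---|---|
| Platelets 51,000 | ≥ 50,000: met | < 30,000: not reached | below 100,000, and below the 75,000 allowed when disease-related | none |
| ANC 600 | ≥ 500: met | < 500: not reached | below 1,000; above the 500 allowed when disease-related | none |
| Platelets 35,000 (contrast) | ≥ 50,000: not met | < 30,000: not reached | below both floors | delay, hence an AE |

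In the first two rows, for a patient with normal counts at baseline, section 6.4 requires neither a hold nor a delay. Unless some other intervention follows, the value becomes an AE, or enters the 7.4.5 summary, only by judgment. Table 6-2 has no hemoglobin, lymphocyte or total white-cell trigger, so those abnormalities enter only through an intervention, some other action or judgment.

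**2. Direction.** For a given abnormality at or above a given grade, let p_A be the share of patients whose value is captured through an action. Let p_S be the share whose value prompts none, and j the fraction of that second group judged significant or relevant.

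- Rate from grading all collected counts: p = p_A + p_S
- Rate after the filter: r = p_A + j × p_S
- Loss: p − r = (1 − j) × p_S

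Since j lies between 0 and 1, the loss lies between 0 and p_S. It cannot be negative.

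**3. Size.** The documents give neither p_S nor j, so the loss cannot be computed. If all 36 planned patients are treated, each patient missed lowers a rate by 1/36 = 0.028, or 2.8 percentage points. Table 1-2 cannot fill the gap. Its thrombocytopenia figure, 68/201 = 34%, is itself a treatment-emergent AE rate from other studies, and the documents do not say what laboratory rule applied there. Multiplying it by an assumed capture fraction could apply the filter twice.

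**The case against.** The strongest reply is that the judgment routes are broad. Section 8.1.1 admits any change the investigator considers significant, and section 8.2 admits any relevant deterioration. To be lost, a marked fall would have to be judged neither. Anemia that is transfused or treated with erythropoietin (both permitted by section 6.6) enters as an intervention. Related Grade 3 non-hematologic toxicity requires a hold under Table 6-3, so it enters too. AEs that lead to discontinuation or dose reduction satisfy the definition automatically. Safety is secondary and descriptive, the primary ORR is untouched, and 7.4.5 does not forbid further tables.

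All of this stands, and it limits the point to values short of the thresholds that prompt no intervention. It does not supply the missing analysis: no graded tabulation is committed to, and the deciding terms are undefined.

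A second reply concerns grading itself. Derived grades carry no attribution, whereas the endpoint includes relatedness. Patients may enter with disease-related cytopenias (section 5.1), so an ANC of 600 may be near baseline. In CLL a fall in blood lymphocytes is part of the response criteria (appendix 11.9). This also stands, and is why the derived tables should accompany the AE tables and not replace them.

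Two stronger inferences are not supported. A reader might take the white-cell example in section 8.1.2, "to less than 2000 is considered Grade 3 (severe) but may not be considered serious", as proof that severe values are dropped. That passage only separates severe from serious and says nothing about exclusion from the AE table. A reader might also suppose that very deep falls routinely go uncounted. As the contrast row shows, platelets of 35,000 on a scheduled Day 1 force a delay and so are captured.

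**Conclusion.** The concern holds in a limited form. Laboratory abnormalities that prompt no discontinuation, delay, dose modification or intervention reach the safety results only through an undefined judgment, and can be absent from both outputs. Relative to grading all collected counts, any bias is downward.

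A reader might go further and conclude that the hematologic rates will be too low. The documents do not support that certainty: if investigators call most abnormal counts significant, the loss is close to zero. They support only that the rates can be too low, by an unknown amount.

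The conclusion assumes that section 6.4 is followed as written, so that values crossing its thresholds do produce the action that makes them AEs. A filtered AE rate is not wrong as an AE rate. It falls short only as a measure of laboratory-defined toxicity. Nor can derived grades recover low points between draws that were never measured. The point is about analysis and takes no position on the dose-modification thresholds.

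**What to change.** In section 7.4.5, replace the summary of clinically significant values with two derived displays for everyone who took at least one dose of ixazomib:

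- worst on-treatment CTCAE 4.0 grade per patient, for each hematology and chemistry parameter;
- shift from baseline grade to that worst grade.

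Derive both from all scheduled and unscheduled CBC and chemistry values, and state which pre-dose value is the baseline and what period counts as on treatment.

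Place these displays beside the AE tables. The AE tables keep the 8.1.1 definition and carry relatedness. Add a note that derived grades carry no attribution, that baseline cytopenias may be due to disease, and that a lymphocyte fall in CLL may be response.

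The cost is a change of wording and one or two programmed tables, with no new tests. Because the Schedule of Events allows local laboratories, the results must all be entered in the study database; if they are not, entering them is added work. The reported rates may look less favorable.
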